3.5.5 Exploratory endpoints

The endpoints related to the 1st exploratory objective are:

- Change from baseline at Weeks 52 and 104 in adaptive behavior composite score as assessed by Vineland Adaptive Behavior Scales, Second edition (VABS-II)

The endpoints related to the 2nd exploratory objective are:

- Population PK model parameter estimates and associated covariates describing intra- and inter-individual variability in respective parameter estimate. The results of these analyses will not be included in the Clinical Study Report for this study, but reported separately.

The endpoints related to the 3rd exploratory objective are:

- Population PK/PD model parameter estimates and associated covariates describing intra- and inter-individual variability in respective parameter estimate. The results of these analyses will not be included in the Clinical Study Report for this study, but reported separately.

4 Study methods

4.1 Overall study design and plan

This is an open, single-arm, multicenter extension study to assess the long-term safety, tolerability and efficacy of SOBI003 in pediatric MPS IIIA patients who previously participated in the (FIH) SOBI003-001 study. Patients completing the FIH study will be offered to participate in the extension study. Please refer to Figure 1 for an overview of the study design. A published natural history study (referred to as the NH study in the present document) is used as external control (**Error! Reference source not found.**). Neurocognitive and adaptive behavior data assessed in the extension study at Week 52 and Week 104 following start of treatment will be compared to available natural history data within the target study population. The natural history population for comparison consists of 14 patients with a rapid progressive MPS IIIA disease and a baseline age of 12 to 72 months.

[figure not shown]
As the FIH study has a sequential, ascending, multiple-dose design, the first patients will enter the extension study (SOBI003-002) before finalization of the FIH study. When entering the extension study, these patients will receive the highest dose that has been declared safe by the

SRC in the ongoing FIH study. Patients enrolled in Cohort 1 of FIH may thus be switched to the dose applied in Cohort 2 or Cohort 3, depending on safety clearance by the SRC. If a patient is initially switched to the dose applied in Cohort 2, the patient may subsequently later be switched to the dose applied in Cohort 3. Depending on recruitment rate in the FIH study, a patient enrolled in Cohort 1 may be directly switched to the dose applied in Cohort 3. Upon completion of the FIH study, an analysis aimed at selecting the dose for forthcoming studies will take place. Once the dose has been selected, this dose will be applied to all patients enrolled in the extension study. The Baseline in SOBI003-001 will be used as the baseline for SOBI003-002 (Figure 1).

SOBI003 is administered as weekly i.v. infusions over a period of time of 1 to 4 hours. Prior to initiation of each infusion, the patients are pretreated with a single dose of non-sedative antihistamine. If infusion-related reactions occur, then the infusion duration may be expanded up to 24 hours and supportive medication may be administered, at the discretion of the investigator.

The long-term safety, tolerability and immunogenicity of SOBI003 will be assessed throughout the extension study whereas measurements of clinical efficacy and disease-related biomarkers will be performed at Weeks 52 and 104. The potential of SOBI003 to improve the neurocognitive function will be compared to published data from the NH study.

Figure 1 Overview for study design for study SOBI003-002

4.2 Selection of study population

The primary aim is to select a study population as close as possible to the NH study.

4.2.1 Inclusion criteria

A patient must fulfill the following criteria in order to be included in the study:

1. Completion of study FIH
2. Informed consent obtained from the patient's legally authorized representative(s)

4.2.2 Exclusion criteria

The presence of the following excludes a patient from inclusion in the study:

1. If, in the opinion of the investigator, there are patient specific safety concerns that contraindicates further treatment with SOBI003

4.3 Method of treatment assignment

4.3.1 Control group

The control group used for the statistical analysis of the DQ endpoint is formed by the 14 patients in the Shapiro Natural History Study with a rapid progressive disease who have a baseline age of 12 to 72 months (Shapiro et al 2016).

4.3.2 SOBI003

All patients in this extension study will receive SOBI003 until 104 weeks after start of treatment unless withdrawn.

5 Sequence of Planned analyses

5.1 Interim Analyses

There is no planned interim analysis for this extension study.

5.2 Analyses and reporting

All final, planned, analyses identified in the protocol and in this SAP will be performed only after the last patient has completed the study.

Any post-hoc analyses included in the CSR, which were not identified in this SAP, will be clearly identified as such in the relevant section of the CSR.

For each patient in the study, all the associated safety and efficacy data in the SOBI003-001 study will be pooled and presented together with the SOBI003-002 study. Thus the SOBI003-001 study and the SOBI003-002 study are considered as a single, unified entity.

6 Estimands

There will be a de facto estimand in the study, which is the primary estimand for the evaluation of efficacy. The estimand is the change in

- cognitive decline in all the patients from the population captured by the inclusion and exclusion criteria (see Section 4.2.1 and Section 4.2.2) and the part of the NH population with a rapid progressive disease having a baseline age of 12 to 72 months, irrespectively of other medications used and adherence to treatment, and estimated by a repeated measures model of the change from baseline in DQ as described in Section 14.1.

- decline in HS levels in CSF in all the patients from the population captured by the inclusion and exclusion criteria (see Section 4.2.1 and Section 4.2.2) irrespectively of other medications used and adherence to treatment, and estimated by a repeated measures model of the change from baseline in HS as described in Section 14.1.

To address foreseeable inter-current events, such as drop-outs, all missing values will be imputed (see Section 14.1) in accordance with the treatment policy principle. A sensitivity analysis will be performed where no imputations are performed, but all values are used: If a patient has a missing value in any assessment, then the same patient's non-missing scores will be used in the repeated measures model. The repeated measures model (see Section 14.1) handles missing values based on the missing at random (MAR) assumption. One further sensitivity analysis for DQ will address this assumption based on zero imputations (see Section 14.1.1), the rationale being that the patients not assessed are those expected to have a severe DQ decline. Other sensitivity analyses for this purpose will be tipping point analyses, see Section 14.1.1.

Furthermore, a principal strata analysis will be performed where only patients without protocol violations will be analyzed according (see Section 14.1.2). In particular patients who did not comply with the dosing scheme but continued the study will be excluded from the analysis. Thus the principal strata will be approximated by the clinical per protocol subset of FAS.

7 Sample size determination

7.1 Change from baseline in DQ score and in HS levels in CSF at 104 weeks

All patients completing the FIH study will be offered to continue into this extension study and the number of patients in the extension study is thus not based on statistical grounds.

However, the 14 patients in the natural history study that will be used as an external control group had a mean baseline DQ of 58.9 points and declined with a mean of 30.4 (SD=12.1) DQ points during 104 weeks. Therefore, assuming very high likelihood of showing significant decrease in HS (with baseline mean of 5.2, std 1.8, correlation of 0.1 and a decrease of 80 % the power is 99 %), with 9 patients treated with SOBI003, the power to demonstrate an improvement in cognitive function is at least 80 % if the decline is reduced from 30.4 to 9.8 DQ points (SD=13.0) and the reduction is homogeneous across age.

8 Analysis sets

The following analysis sets will be used in the statistical analyses and exploration of data.

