### **7.3 Selection of study population**

#### **7.3.1 Inclusion criteria**

A patient must fulfill the following criteria in order to be included in the study:

1. Completion of the FIH study ([SOBI003-001](#))
2. Informed consent obtained from the patient's legally authorized representative(s)

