8.1 Safety analysis set

The Safety analysis set will consist of all patients in the study. For each patient in the study, all the associated safety and efficacy data in the SOBI003-001 study will be pooled and presented together with the SOBI003-002 study. The safety set will be used for the safety presentations.

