8.2 Full-analysis set

The full-analysis set (FAS) is the efficacy analysis set which will consist of all patients enrolled in this extension study, and all patients in the NH study with a rapid progressive disease having a baseline age of 12-72 months (in the DQ analyses).

All patients enrolled in this extension study and the FIH study will be treated as having received active treatment and patients from the NH study will be treated as having received no treatment. For each patient in the study, all the associated safety and efficacy data in the SOBI003-001 study will be pooled and presented together with the SOBI003-002 study.

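### Pooled Week 0–104 safety and DQ results start at the FIH baseline but include only FIH completers who enrolled in the extension, creating a risk of selection (immortal-time) bias of unknown size

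*SAP*

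**What the plan says.** **Time zero.** SAP 4.1: "The Baseline in SOBI003-001 will be used as the baseline for SOBI003-002". Protocol section 6 likewise takes the FIH baseline for efficacy.

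**Entry.** The first inclusion criterion is "Completion of the FIH study" (Protocol 7.3.1), or "Completion of study FIH" (SAP 4.2.1). The only exclusion criterion applies when, in the investigator's opinion, "there are patient specific safety concerns that contraindicates further treatment with SOBI003" (SAP 4.2.2; Protocol 7.3.2 matches). Both are judged at about Week 25.

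**Pooling.** SAP 5.2: "For each patient in the study, all the associated safety and efficacy data in the SOBI003-001 study will be pooled and presented together" with the extension data. It then concludes: "Thus the SOBI003-001 study and the SOBI003-002 study are considered as a single, unified entity".

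**Analysis sets.** SAP 8.1: "The Safety analysis set will consist of all patients in the study". SAP 8.2 defines the FAS as the efficacy set, "which will consist of all patients enrolled in this extension study", plus the natural history (NH) controls for DQ. Two sentences blur this. Protocol 9.2 defines the safety set as anyone given a dose of study drug. SAP 8.2 also has a sentence that assigns active-treatment status to patients enrolled in the extension and the FIH study.

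**Safety tables.** SAP 15.2 counts an event as treatment-emergent from first exposure, which took place in the FIH study. Its overview table has rows for events leading to death and to study discontinuation.

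**The concern.** A patient's clock starts at the FIH baseline, but whether that patient is counted depends on what happened over the next 24 weeks. A child who died, withdrew or stopped because of intolerance before completing the FIH study never enters the set, and the second entry criterion selects directly on safety. This is the usual structure of immortal-time bias.

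Safety is the primary objective, and Protocol 5.2 expects that hypersensitivity and infusion reactions, some severe, may occur. An early reaction that ends treatment is the kind of event the rule would drop. A reader of a two-year table built on two studies described as one would not know that the first 24 weeks could contain no death and no study withdrawal.

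The DQ comparison in SAP 14.1 uses the same treated patients. The selection would also carry forward: SAP 17 plans to take a subpopulation of this FAS into the Phase III primary analysis.

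**Working it through.** **1. The plan's own figures.** SAP 7.1 gives 14 controls with mean baseline DQ 58.9 and mean decline 30.4 (SD 12.1), and 9 treated patients with an assumed decline of 9.8 (SD 13.0). The planned difference is 30.4 − 9.8 = 20.6.
- DQ: a two-sided 5% t test, 9 vs 14, SD 13.0 and 21 df, has power 0.94, consistent with the stated lower bound of 80%.
- HS: the mean change is 0.8 × 5.2 = 4.16 and the SD of change is 1.8 × √(2 × 0.9) = 2.415. With n = 9 the paired t test has power 0.994, matching the stated 99%.

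These figures are not in dispute. They only supply the inputs below.

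**2. Who can be in the tables.** Set SAP 4.1 (baseline), 4.2 (entry), 5.2 (pooling), 8.1 and 8.2 (sets) side by side. FIH records enter only through a patient who is in the extension. For Weeks 1–24 the death and study-discontinuation counts are therefore zero whatever happened in the FIH study.

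**3. Whether planned analyses repair this.** The imputation in SAP 14.1 and the DQ = 0 and tipping-point analyses in SAP 14.1.1 replace missing values of patients already in the set. They cannot add a patient. SAP 15.1 and 16.1 plan exposure and PK both for the extension alone and pooled; no such split is planned for adverse events.

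**4. Illustrative size.** The number of FIH non-completers, k, is not in the documents, so I assume 0 to 3. The extension plans 9 to 12 patients (Protocol synopsis). With n extension patients declining by 9.8 and k non-completers declining by D:

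shift in treated mean decline = k × (D − 9.8) / (n + k)

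Decline D for a non-completer:
- Like completers: D = 9.8, so the shift is 0 for any k.
- SAP 14.1 imputation, assuming linear slopes and only a baseline DQ (treated slope before stopping, untreated slope after):
  - stop at Week 12: 9.8 × 12/104 + 30.4 × 92/104 = 1.13 + 26.89 = 28.0
  - stop at Week 24: 9.8 × 24/104 + 30.4 × 80/104 = 2.26 + 23.38 = 25.6
- Like NH controls throughout: D = 30.4.
- DQ = 0 with a baseline of 58.9: D = 58.9.

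For n = 9 and k = 1:
- stop at Week 24: (25.6 − 9.8)/10 = 1.6
- stop at Week 12: (28.0 − 9.8)/10 = 1.8
- NH decline: (30.4 − 9.8)/10 = 2.06, so the mean decline is 11.86
- DQ = 0: (58.9 − 9.8)/10 = 4.91

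Shift in DQ points for k = 1 / 2 / 3:

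| n | NH-like decline | DQ = 0 |
|---|---|---|
| 9 | 2.06 / 3.75 / 5.15 | 4.91 / 8.93 / 12.28 |
| 12 | 1.58 / 2.94 / 4.12 | 3.78 / 7.01 / 9.82 |

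Early discontinuation, pooled set against all FIH-dosed patients, for k = 1 / 2 / 3:
- n = 9: 0/9 against 1/10 (10.0%), 2/11 (18.2%), 3/12 (25.0%)
- n = 12: 0/12 against 1/13 (7.7%), 2/14 (14.3%), 3/15 (20.0%)

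**The case against.** **No loss is documented.** Neither document gives the number of FIH patients enrolled, the number who left, or their outcomes. A reader might infer that safety and efficacy do look better than they are. That needs at least one omitted patient with worse outcomes, and nothing shows there was one. This objection stands and limits the point to a risk.

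**The controls may be selected too.** Protocol 9.4.4.1 describes the 14 NH patients as having 24 months of follow-up. If they were chosen for that, their condition is longer than 24 weeks and could offset some or all of the DQ bias. SAP 8.2, which takes all eligible NH patients, and the tipping-point analysis, which allows for missing control values, leave this open. The objection stands for DQ. It does not help the safety tables, which have no comparator.

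**The estimand.** A reader might also see a contradiction between an estimand that disregards adherence and an entry rule that requires FIH completion. The documents do not support that: SAP 6 defines the population by the extension's entry criteria, and disregard of adherence applies within that population.

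**The early weeks are not empty.** Completers' own adverse events and non-fatal SAEs from Weeks 1–24 are pooled in. Only death and study discontinuation are zero by construction, and those occurring from Week 25 on still count. This stands; the events of non-completers remain missing.

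**Power barely moves.** With the full 2.06-point shift, 10 vs 14 patients and SD 13, power is about 0.91, still above the stated bound. That is correct, but the issue is bias and labelling rather than power.

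**The set wording may already include everyone dosed.** The Protocol 9.2 safety definition could be read that way. The SAP 8.2 sentence reads as a rule for labelling treatment, and SAP 8.1 points the other way. That is a reason to reconcile them.

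**Conclusion.** The structural point holds: time zero is the FIH baseline, membership is decided at about Week 25, and under the SAP no planned analysis brings in patients lost between the two. In the pooled tables, deaths and study discontinuations in Weeks 1–24 are zero by design, and FIH non-completers' TEAEs and SAEs are absent.

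The consequence is a risk of selection bias of unknown size. For safety it probably favours SOBI003. For DQ a favourable bias is possible but not established, given the uncertainty over how the controls were selected. It is zero if every FIH patient completed and enrolled, and the DQ part is also zero if those lost declined like completers. With one assumed non-completer beside 9 completers and a decline of 25.6 to 30.4, the DQ shift is about 1.6 to 2.1 points, or 8% to 10% of the planned 20.6. Larger figures require more non-completers or the DQ = 0 convention. It should be corrected because the documents neither acknowledge the selection nor plan an analysis that would reveal it.

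**What to change.** 1. Define the pooled Week 0–104 safety tables on all patients dosed in SOBI003-001. Failing that, show Week 25–104 adverse-event tables separately and label the pooled ones *FIH completers who enrolled*.
2. Report the number of FIH non-completers, and of completers who did not enrol, with reasons.
3. Add a DQ sensitivity analysis from the FIH baseline in all FIH-dosed patients with a baseline DQ, using the imputation rule in SAP 14.1.
4. Reconcile the safety-set and FAS wording in Protocol 9.2, SAP 8.1 and SAP 8.2, and state whether the NH controls were selected on 24-month follow-up.

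The cost is SAP wording, a few more tables and some additional SOBI003-001 records. Whether consent and post-withdrawal follow-up in that study allow all of this cannot be checked from these documents; the labelling option and the reconciliation of definitions do not depend on it. Figures may become slightly less favourable. If nobody was lost, the results do not change.

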8.1 Safety analysis set

The Safety analysis set will consist of all patients in the study. For each patient in the study, all the associated safety and efficacy data in the SOBI003-001 study will be pooled and presented together with the SOBI003-002 study. The safety set will be used for the safety presentations.

8.2 Full-analysis set

The full-analysis set (FAS) is the efficacy analysis set which will consist of all patients enrolled in this extension study, and all patients in the NH study with a rapid progressive disease having a baseline age of 12-72 months (in the DQ analyses).

All patients enrolled in this extension study and the FIH study will be treated as having received active treatment and patients from the NH study will be treated as having received no treatment. For each patient in the study, all the associated safety and efficacy data in the SOBI003-001 study will be pooled and presented together with the SOBI003-002 study.

8.3 PK analysis set

The PK analysis set will consist of those patients in the safety analysis set who have at least one SOBI003 serum concentration value, without any protocol deviation jeopardizing the PK evaluation. For each patient in the study, all the associated safety and efficacy data in the SOBI003-001 study will be pooled and presented together with the SOBI003-002 study.

The PK analysis set will be used for the PK analyses.

8.4 Immunogenicity analysis set

The immunogenicity set will consist of those patients in the safety set who have sufficient blood samples taken for ADA testing at baseline (screening visit) and at least one post-dose time-point.

For each patient in the study, all the associated safety and efficacy data in the SOBI003-001 study will be pooled and presented together with the SOBI003-002 study.

The immunogenicity set will be used for the immunogenicity analyses.

9 General issues for statistical analysis

All statistical tests will be two-sided and performed using a 5 % significance level, if not stated otherwise. Results will be presented as the estimated mean value for each treatment group, the estimated difference between groups, the associated 95 % two-sided confidence interval and P-value. P-values from statistical analyses will be presented to three decimal places with values below 0.001 displayed as <0.001 and confidence intervals will be presented to one more decimal places than the raw data.

Continuous data will be summarized using descriptive statistics: n, mean, standard deviation (SD), standard error of the mean (SE), median, minimum and maximum, unless otherwise indicated. Minimum and maximum will be presented to the same number of decimal places as the raw data and mean, standard deviation, standard error of the mean and median will be presented to one more decimal place than the raw data.

Categorical data will be summarized using counts and percentages. Percentages will be suppressed when the count is zero, however the category will still be displayed. The denominator for all percentages will be the number of patients within the treatment group for the population of interest, unless otherwise indicated. Percentages will be presented to one decimal place.

All data will be tabulated in individual patient data listings.

Statistical analyses will be performed using SAS software (SAS Institute Inc, Cary, North Carolina, United States).

9.1 Handling of missing data

All missing DQ values and HS in CSF values will be imputed. The procedure is fully described in Section 14.1. A sensitivity analysis will be performed where no imputations are performed, but all values are used: If a patient has a missing DQ score in any assessment, then the same patient's non-missing scores will be used in the repeated measures model. The repeated measures model (see Section 14.1) handles missing values based on the MAR assumption. One further sensitivity analysis will address this assumption based on zero imputations (see Section 14.1.1), the rationale being that the patients not assessed are those expected to have a severe DQ decline. Another sensitivity analysis for this purpose will be a tipping point analysis, see Section 14.1.1.

If an adverse event (AE) has a completely missing onset date, then the AE will be considered a TEAE, unless the (partial) stop date indicates differently. A medication with a completely missing start date is considered a prior medication. A medication with a completely missing stop date is considered a concomitant medication. If an AE or a medication has a partial missing start or stop date, the following rules will be used to impute the date. The imputed date will be used to determine whether it is a TEAE for adverse event, or a prior or concomitant medication.

Table 1 Partial date derivation

Partial Missing Start or Stop Date	Derived Start Date	Derived Stop Date
Missing month and day, and the year is present	January 1 st of that year or first dose date if the year is the same as the year of first dose date	December 31 st of that year

Partial Missing Start or Stop Date	Derived Start Date	Derived Stop Date
Missing day, but year and month are present	First day of that month or first dose date if the year and month are the same as the year and month of first dose date	Last day of that month
Missing month, but year and day are present	Missing month derived as January or same as first dose month if the year is the same as the year of first dose	Missing month derived as December

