11.3 Medical history

Medical and surgical history will be coded using the Medical Dictionary for Regulatory Activities (MedDRA) (version 16.1 or higher). All medical history events will be listed by system organ class (SOC) and preferred term. Surgical history will be presented in a separate listing.

12 Prior and concomitant medication

All prior and concomitant medication will be coded using the latest version of World Health Organization drug dictionary (WHO Drug) version June 1 2013.

Prior medications are defined as those for which the end date is prior to Day 1. Concomitant medications are defined as those which are indicated as ‘Ongoing’ on Day 1, those which start on or after Day 1 and those which start prior to Day 1 and have an end date on or after Day 1.

If medication dates are incomplete and it is not clear whether the medication was concomitant, it will be assumed to be concomitant.

The number and percentage of patients who took any concomitant medications will be presented by medication class and standardized medication names sorted alphabetically.

All prior and concomitant medications will be listed by reported name, medication class, standardized medication name, indication, dose, dose unit, frequency, route of administration, start date and end date or ‘ongoing’ flag and duration of use. Concomitant medications will be flagged.

13 Treatment compliance

There will be no measurement of, or analysis of, treatment compliance, nor does it affect population assignment (patients must be exposed to IMP to qualify for the analysis sets).

14 Efficacy analyses

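### SAP 9.1 and SAP 12 classify a medication with a completely missing start date by conflicting rules, so use during treatment can be left out of the concomitant-medication table

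*SAP*

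**What the plan says.** Two parts of the SAP decide whether a medication is prior or concomitant.

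**SAP 9.1 (Handling of missing data)** has two sentences for completely missing medication dates. For the start date: "A medication with a completely missing start date is considered a prior medication". For the stop date: "A medication with a completely missing stop date is considered a concomitant medication". Partial dates are handled separately: "If an AE or a medication has a partial missing start or stop date, the following rules will be used to impute the date". Those rules are in SAP Table 1. For an adverse event with no onset date at all, the same section says: "then the AE will be considered a TEAE, unless the (partial) stop date indicates differently".

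**SAP 12 (Prior and concomitant medication)** gives the definitions. "Prior medications are defined as those for which the end date is prior to Day 1". A medication is concomitant if it is ongoing on Day 1, starts on or after Day 1, or starts earlier and ends on or after Day 1. There is also a default: "If medication dates are incomplete and it is not clear whether the medication was concomitant, it will be assumed to be concomitant".

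On reporting, Section 12 says: "The number and percentage of patients who took any concomitant medications will be presented by medication class". Prior medications get no such table. Both kinds go into a listing, in which the concomitant ones are flagged.

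**The concern.** The two sections answer the same question differently. Section 12 makes the end date decisive for prior status. Section 9.1 assigns prior status from the absence of a start date alone, even when a recorded stop date shows that the drug was taken during treatment. Neither section refers to the other or claims precedence, so two programmers could produce different tables from the same data.

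What is at stake is the description of co-treatment. Protocol 7.4.6 requires therapy used between enrolment and study completion to be recorded, and it permits melatonin and continued low-dose genistein. It is an assumption, though a plausible one, that start dates are more often unknown for drugs begun long before the study. If so, the 9.1 rule falls on drugs that are likely to be in use on treatment.

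**Working it through.** The plan gives no figure to reproduce. The check takes a medication whose start date is completely missing and applies each rule to every possible state of the end date.

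1. **End date before Day 1.** 9.1: prior. Section 12: prior. They agree.
2. **End date on or after Day 1.** 9.1: prior. Section 12: concomitant whatever the true start, because a start before Day 1 with this end is concomitant and so is a start on or after Day 1. They conflict.
3. **Flagged as ongoing.** 9.1: prior, if the flag is not treated as a missing stop date. Section 12: concomitant. They conflict. If the flag is treated as a missing stop date, 9.1 gives the result in case 4.
4. **End date also completely missing.** 9.1: prior by its start-date sentence and concomitant by its stop-date sentence, so it contradicts itself. Section 12: unclear, hence concomitant by default.

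The rules agree in 1 of the 4 cases.

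A partial end date adds no further case. Table 1 moves it to the latest date consistent with the known part, and the record then falls under case 1 or case 2.

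Two comparisons within 9.1 suggest an oversight rather than a deliberate choice:

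- The adverse-event rule leans towards on-treatment status and lets the stop date overrule it. The medication rule leans the other way and has no such override.
- For a partial start date in the same year as the first dose, with the month missing or matching that of the first dose, Table 1 leans towards the first dose. When the date is missing altogether, the lean reverses to prior.

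**Size.** The protocol synopsis plans 9 to 12 children. If one child is wrongly dropped from a row of the table, and has no other record that counts in that row, the percentage changes by:

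- 1/12 = 8.3 percentage points with 12 children
- 1/9 = 11.1 percentage points with 9 children

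This is the effect of one child, not a forecast. The documents do not say how many records will lack a start date.

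**The case against.** The strongest reply is that the gap is narrow and little is lost.

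- **Scope.** A reader might take the rule to cover every missing start date. It does not. If only the year is known, Table 1 supplies a start date and Section 12 then applies. This stands.
- **Typical chronic drugs.** Protocol 7.4.6 prefers unaltered regimens, so a long-standing drug will often have no stop date or an ongoing flag. The stop-date sentence in 9.1, or Section 12, then points to concomitant. This stands in part: it lowers the likely number of affected records. It does not settle the order of the rules, because the start-date sentence in 9.1 still says prior for the same record.
- **Section 12 as the rescue.** Its default could be read as correcting 9.1. But the default applies only where status is unclear, and 9.1 purports to settle the status.
- **Nothing disappears.** The listing shows each drug with its dates or ongoing flag, and in a study this small a reader can find an on-study stop date. This stands. Only the table count and the flag would be wrong. A row for any concomitant medication would hardly move, since every child receives a recorded antihistamine before each infusion.
- **Efficacy.** A reader might infer that misclassified genistein or melatonin biases the HS or sleep results. The documents do not support that. They draw no link between genistein and HS. The DQ, HS and MRI models in SAP 14.1, 14.2 and 14.5 do not include concomitant medication, and sleep is only summarised descriptively (SAP 14.7). SAP 6 defines the estimand regardless of other medications.

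**Conclusion.** The conflict is real and confined to records with a completely missing start date. For those ending on or after Day 1, or flagged as ongoing (unless the flag is handled as a missing stop date), 9.1 and Section 12 give opposite answers. For those with no end date either, 9.1 gives both answers. Following the start-date sentence in 9.1 would drop a drug with use on or after Day 1 from the only medication table and remove its flag in the listing.

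The consequence is minor: descriptive reporting only, with the DQ and HS tests untouched. A larger figure, such as the combined shift from several children, might be inferred from the per-child arithmetic, but it would rest on an invented count. The conclusion rests on the wording of the two sections and on the absence of any stated precedence. It does not depend on how many start dates turn out to be missing.

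**What to change.** Either of two edits to SAP 9.1 is enough:

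- delete the start-date sentence for medications and refer to Section 12; or
- replace it with a rule that a medication is prior only if its end date, imputed where partial, falls before Day 1, and is otherwise concomitant, including when the start date is missing.

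Keep the reference to Day 1 in Section 12 and define it, because the SAP does not say which day is meant. SAP 5.2 treats SOBI003-001 and SOBI003-002 as one entity, and Table 1 in SAP 9.1 refers to the first dose date. Protocol 7.5.1.2, however, captures concomitant medication from Day 1 of Week 25. A drug that started and ended between the first SOBI003-001 dose and Week 25 is concomitant on one reading and prior on the other. The SAP should state which is intended. Replacing Day 1 with the first dose without saying so would make that choice silently.

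The cost is one or two sentences in the SAP, with no new data. The programming specification should follow the single rule.
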